Study Protocol and Statistical Analysis Plan

Official Title: Metacognitive Therapy and Intolerance-of-Uncertainty Therapy for Generalized Anxiety Disorder in Primary Care: Randomized Controlled Pilot Study

NCT Number: NCT03621371

Document Date: 4 July 2024

Study Protocol

Objective. Feasibility and preliminary efficacy of two psychological treatments based on cognitive-behavioral therapy – metacognitive therapy (MCT) and intolerance-of-uncertainty therapy (IUT) – for primary care patients with a principal diagnosis of generalized anxiety disorder in Stockholm, Sweden are investigated in a pilot study using a randomized controlled trial design. The purpose of the study is to examine the feasibility of a full-scale randomized controlled trial. Design. Randomized controlled pilot trial. Methods. Research questions primarily concern recruitment, assessment, and therapist competence and adherence. Secondary research questions concern treatment efficacy. Primary treatment outcome measure is total scores on the Penn State Worry Questionnaire (PSWQ).

Statistical Analysis Plan

Statistical analyses are performed using the SPSS (Version 27, SPSS Inc., Chicago, IL). Proportions, means, and standard deviations (SDs) are calculated for feasibility measures. Differences in session attendance between the IUT and MCT conditions are investigated using an independent t-test and differences in dropout with a Fisher's exact test. In the preliminary evaluation of treatment effects, multilevel modeling is used to estimate the effects of time and of time by condition on continuous outcome measures from the pre-treatment to the post-treatment assessment and from the post-treatment to the follow-up assessment. The maximum likelihood method is used to estimate model parameters. Different covariance structures are tested. Models are built in a stepwise fashion, starting with a basic model with a fixed intercept, then adding random parameters (intercept and slope), and finally adding a time by group interaction term to the model. Each model's fit to observed data is evaluated with the likelihood ratio test. Models with significantly better fit than previous models are retained. Standardized effect sizes for between-group effects at mid-treatment, post-treatment,

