and follow-up are calculated as Cohen's d for multilevel models, using the SD for the pooled sample at pre-treatment and the pooled sample SD at post-treatment (for post-treatment to follow-up). For between-group effect size estimations, the beta coefficient (difference in change trajectories between treatments) is multiplied by treatment duration at mid-treatment, the average treatment duration, or the follow-up duration, and then divided by the pooled SD of observed values at pre-treatment or post-treatment. For model-based d , 95% confidence intervals are calculated. In keeping with the principle of intention-to-treat, data from all participants are used in the multilevel models.

Treatment response is assessed with the reliable change index (RCI), which is calculated using the internal consistency reliability of the PSWQ and the sample SD of this measure at pre-treatment. An RCI of $z \geq -1.96$ indicates reliable improvement, whereas an RCI of $z \geq 1.96$ indicates reliable deterioration. Differences in improvement and deterioration between conditions at the post-treatment and follow-up assessment are investigated with chi-square tests or Fisher's exact tests.

To assess recovery rates, two procedures are employed that combine statistically reliable change with clinically meaningful change. First, an RCI of 7 points and a cut-off of 53 points on the PSWQ as used in a previous study are applied. Second, the same RCI and a cut-off of 47 points as used in another previous study are applied. Differences in recovery rates between groups at post-treatment and follow-up assessment are investigated with chi-square tests or Fisher's exact tests.

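### The inequality for reliable improvement on the PSWQ points the wrong way, so unchanged and worsened patients count as improved and clear improvers do not

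*Combined protocol and SAP*

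**What the plan says.** The Study Protocol section names the outcome: "Primary treatment outcome measure is total scores on the Penn State Worry Questionnaire (PSWQ"). In the Statistical Analysis Plan, the paragraph on treatment response bases response on the reliable change index (RCI), "calculated using the internal consistency reliability of the PSWQ and the sample SD of this measure at pre-treatment". The plan gives no value for the reliability or the SD, and it does not write out the difference (later minus earlier, or the reverse).

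The classification rule is: "An RCI of $z \geq -1.96$ indicates reliable improvement, whereas an RCI of $z \geq 1.96$ indicates reliable deterioration".

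The resulting classes are then compared between arms: "Differences in improvement and deterioration between conditions at the post-treatment and follow-up assessment are investigated with chi-square tests or Fisher's exact tests".

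The next paragraph defines recovery separately, with a reliable-change criterion in PSWQ points: "First, an RCI of 7 points and a cut-off of 53 points on the PSWQ as used in a previous study are applied". A second version keeps the 7 points and uses a cut-off of 47. The 7 points carry no sign, so this paragraph does not settle the direction of the response rule.

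**The concern.** Improvement and deterioration are opposite outcomes, so their critical regions should lie in opposite tails and should not overlap. Here both inequalities point the same way, and the region labelled improvement contains the whole of the region labelled deterioration.

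This sentence is the plan's only definition of treatment response, and it applies to the primary treatment outcome measure. An analyst who followed it would report wrong response rates at post-treatment and follow-up, and the arm with more true improvement would show the lower response rate.

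**Working it through.** **Inputs from the plan.** Improvement: z ≥ −1.96. Deterioration: z ≥ 1.96. Both come from the treatment-response paragraph of the Statistical Analysis Plan.

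**The critical value.** The two-sided 5% standard normal quantile is 1.95996, which rounds to 1.96. The size of the threshold is right; only the direction is in question.

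**Sign convention.** Deterioration at z ≥ 1.96 means worsening is positive, so improvement lies in the negative tail. Applying both rules on that scale:

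| z | As written | With improvement at z ≤ −1.96 |
|---|---|---|
| −4, −3, −1.97 | neither | improved |
| −1.96 | improved | improved |
| −1.95, −1, 0, 1 | improved | no reliable change |
| 1.96, 3 | improved and deteriorated | deteriorated |

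Only a patient at exactly z = −1.96 is classed as improved under both rules.

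**The opposite convention.** If positive z meant improvement, the printed deterioration rule would pick out the patients who improved most. The printed improvement rule would still include unchanged patients, and the overlap would remain. Neither convention makes the sentence valid.

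**Size in standard-error units.** Assume RCI ~ N(μ, 1), where μ is the true change in standard errors of the difference and negative means improvement. With Φ the standard normal distribution function:

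- as written, P(improved) = 1 − Φ(−1.96 − μ)
- corrected, P(improved) = Φ(−1.96 − μ)

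| μ | As written | Corrected |
|---|---|---|
| 0 | 0.975 | 0.025 |
| −1 | 0.832 | 0.169 |
| −1.96 | 0.500 | 0.500 |
| −3 | 0.149 | 0.851 |
| −4 | 0.021 | 0.979 |
| +2 (true worsening) | 1.00 | 0.00 |

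The two rates are complements, apart from rounding.

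**Direction of the arm comparison.** Suppose one arm has μ = −3 and the other μ = −1.96. The correct difference in improvement rates is 0.851 − 0.500 = +0.351 in favour of the first arm. As written it is 0.149 − 0.500 = −0.351.

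**Size in PSWQ points (illustration only).** Assume change ~ N(−12, SD), SD of change 8 or 10, and a 7-point threshold. The plan gives no mean or SD. The 7 points are borrowed from the recovery rule.

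- SD 8: (−7 + 12)/8 = 0.625, so P(change ≤ −7) = 0.734; as written, 1 − 0.734 = 0.266.
- SD 10: (−7 + 12)/10 = 0.5, so P(change ≤ −7) = 0.691; as written, 1 − 0.691 = 0.309.

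The trial's own threshold in points would be 1.96 × SD × √(2(1 − r)), with SD taken at pre-treatment and r the reliability. At SD 8 and r 0.90 that is 7.01. Over assumed SDs of 6 to 12 and reliabilities of 0.80 to 0.93 it runs from 4.4 to 14.9. The percentages would move with it, but the written rate remains one minus the correct rate.

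**The case against.** The strongest case on the other side accepts the error and argues that it matters little.

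- **Secondary analysis.** Efficacy is a secondary question in this feasibility pilot, and response is one dichotomised analysis within it. The multilevel models do not use the rule, and the recovery analyses have their own 7-point criterion. This stands and limits the reach of the problem.
- **The p-value would not change.** Apart from z exactly −1.96, the printed improved group is the complement of the correct one. A two-sided chi-square or Fisher's exact test is unaffected by swapping the two outcome columns. This is true, but the reported rates and the favoured arm would still flip, and the p-value would give no warning of it.
- **Deterioration is unaffected.** On the plan's own convention z ≥ 1.96 is the right cut-off, so the deterioration comparison is sound taken alone. This stands. What fails is the improvement class, and with it any clean table of improved, unchanged and deteriorated patients.
- **It is probably a slip.** The contrast in the sentence and the symmetric ±1.96 make the intent fairly plain, and an analyst coding it literally would probably notice patients in both classes. Nothing shows that it was coded literally. A symbol misread from the PDF cannot be fully excluded either, though nothing in the text points to one. This makes actual harm less likely; it does not make the printed rule usable.
- **Reference point at follow-up.** The plan does not say whether response at follow-up is measured from pre-treatment. An index built on the pre-treatment SD points that way, but the authors should confirm it.

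**Conclusion.** The concern holds. The improvement rule is wrong as printed under either sign convention, and no other part of the document corrects it. If applied literally, it would report one minus the true improvement rate (apart from a patient at exactly z = −1.96) and reverse which arm appears better. That reversal follows from the inequalities alone. The 97.5% versus 2.5% contrast assumes only a standard normal RCI under no true change. The 69–73% versus 27–31% contrast rests on an assumed mean, SD and threshold and is not an estimate for this trial.

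The damage is confined to the improvement classification and its comparison between arms, and it arises only if the rule was coded as written. Because the sentence is a stated decision threshold on the primary treatment outcome measure, it should be corrected even though the intended rule is easy to guess.

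**What to change.** Replace the sentence with a rule that states the direction of the difference and gives three exclusive categories, for example:

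> The RCI is the post-treatment (or follow-up) score minus the pre-treatment score, divided by the standard error of the difference. z ≤ −1.96 indicates reliable improvement, z ≥ 1.96 indicates reliable deterioration, and −1.96 < z < 1.96 indicates no reliable change.

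This wording takes higher PSWQ scores as worse, in line with deterioration at positive z, and uses pre-treatment as the reference at both assessments. The authors should confirm both points.

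Then check that the SPSS recode produces these three categories and that no patient falls in two. If response rates have already been produced, confirm which rule generated them.

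The cost is one sentence in the plan and a short syntax check, with no effect on design, data collection or the other analyses.

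### The printed threshold for reliable improvement on the PSWQ has its inequality reversed: z ≥ −1.96 should read z ≤ −1.96

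*Combined protocol and SAP*

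**What the plan says.** The Statistical Analysis Plan's paragraph on treatment response classifies participants with a reliable change index (RCI), "which is calculated using the internal consistency reliability of the PSWQ and the sample SD of this measure at pre-treatment". It gives two decision rules on the same z scale: "An RCI of $z \geq -1.96$ indicates reliable improvement", and "an RCI of $z \geq 1.96$ indicates reliable deterioration". Improvement and deterioration are then compared between conditions at post-treatment and follow-up, with chi-square or Fisher's exact tests.

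The next paragraph, on recovery, says that "two procedures are employed that combine statistically reliable change with clinically meaningful change". The first procedure applies "an RCI of 7 points and a cut-off of 53 points on the PSWQ as used in a previous study". The other is introduced with "Second, the same RCI and a cut-off of 47 points", also credited to earlier work. The plan gives no reliability value, no pre-treatment SD and no written-out formula for the RCI.

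**The concern.** Two cut-points on one index should mark off opposite tails, with the unchanged participants between them. Here both inequalities point the same way. Every z that meets the deterioration rule also meets the improvement rule, and so does every z between −1.96 and 1.96. The only participants whom the improvement rule excludes are those with z below −1.96, who improved most. If the rule were programmed as printed, the response rates would be wrong in both arms and the comparison between conditions would point the wrong way.

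A smaller matter is that the recovery paragraph uses the label RCI again, for a fixed number of points taken from a previous study, without saying how that number relates to the index just defined.

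**Working it through.** **1. Direction of z.** The deterioration rule fixes it: large positive z is worse, so large negative z is better. No sign convention rescues the printed pair. The set z ≥ 1.96 lies wholly inside the set z ≥ −1.96, whichever way the difference is taken.

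**2. Three example participants.** The plan prints no formula, so I assume the usual one, z = (post − pre) / [SD × √(2(1 − r))], where r is the reliability. With assumed SD 9 and r 0.85, the denominator is 9 × √0.30 = 4.93.

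| Change in PSWQ | z | Printed improvement rule (z ≥ −1.96) | Intended rule (z ≤ −1.96) | Deterioration rule (z ≥ 1.96) |
|---|---|---|---|---|
| −15 | −15/4.93 = −3.04 | not improved | improved | no |
| 0 | 0 | improved | not improved | no |
| +12 | 12/4.93 = 2.43 | improved | not improved | yes |

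The third participant would be both improved and deteriorated.

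**3. Effect on rates.** Apart from a z of exactly −1.96, the printed set is the complement of the intended one. If the intended improvement proportions in the two arms are p₁ and p₂, the printed rule yields 1 − p₁ and 1 − p₂. The difference becomes (1 − p₁) − (1 − p₂) = −(p₁ − p₂): same size, opposite sign. The two-sided chi-square or Fisher p-value does not change, because the table's two columns are only swapped. The error therefore lies in the rates and in the direction of the comparison. For a participant with no true change and z standard normal, P(z ≥ −1.96) = Φ(1.96) = 0.975, against P(z ≤ −1.96) = 0.025.

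**4. The 7 points (minor).** In points, the sample-based threshold is 1.96 × SD × √(2(1 − r)). Setting this equal to 7 gives SD × √(1 − r) = 7/(1.96 × √2) = 2.525. The plan's 7 cannot be reproduced, since neither SD nor r is given. Over assumed values:

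| r | SD 8 | SD 9 | SD 10 |
|---|---|---|---|
| 0.85 | 8.59 | 9.66 | 10.74 |
| 0.90 | 7.01 | 7.89 | 8.77 |
| 0.95 | 4.96 | 5.58 | 6.20 |

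The sample threshold can thus lie above, at or below 7. The share of participants classified differently is P(drop lies between 7 and the sample threshold, and post score is past the cut-off). I assumed normal scores, baseline mean 60 to 70, change with mean −10 and SD 10, baseline-change correlation 0 or −0.4, and the SD and r values in the table. The share then runs from 0 to about 10% at cut-off 53 and from 0 to about 6% at cut-off 47. The upper ends come from r = 0.85 with whole-number scores and a cut-off read as at or below. All these inputs are assumptions.

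**The case against.** The strongest reply on the sign is that it is plainly a slip. The minus sign shows what was meant, and an analyst would code the lower tail without a second thought. That is probably true, and it limits the practical risk. It does not make the text right: this is the plan's only decision rule for reliable improvement, and it is incorrect as it stands. A reader might go further and infer that the trial's response rates are wrong. The document does not support that, because it contains no results and no code.

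On the 7 points, the reply is largely correct. Response and recovery are separate outcomes, each has one stated criterion, and the 7 points are openly attributed to a previous study. Published criteria are legitimate and aid comparison. A fixed value also avoids the sampling error of a pilot SD. With SD 9, r 0.85 and an assumed N of 20, the sample threshold of 9.66 has a 95% sampling range of 9.66 × √(χ² quantile/19), about 6.6 to 12.7 points, which includes 7.

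A reader might infer from the shared label that the two paragraphs contradict each other, or that some recovered participants will lack reliable change. Neither follows. A participant could be recovered without meeting the trial's own RCI only if the sample threshold exceeds 7, and the document does not show whether it does. If the threshold is below 7, the discrepancy runs the other way: some reliably improved participants past the cut-off would miss recovery only through the 7-point rule. At SD 8 and r 0.90 the two nearly coincide, at 7.01 against 7. What stands is one unexplained label.

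**Conclusion.** The improvement threshold is wrong as written. This rests on the text alone and needs no assumed figure: with z ≥ 1.96 as deterioration, z ≥ −1.96 cannot define improvement. Followed literally, it would give the complement of each arm's improvement rate and reverse the direction of the between-condition difference at both assessments. The 97.5% against 2.5% for an unchanged participant assumes a standard normal z.

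The reach is limited. The protocol says "Secondary research questions concern treatment efficacy", and the multilevel analysis of continuous scores does not use this rule. The printed deterioration rule is sound, and the recovery criteria do not use the z rule.

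The double use of RCI is a point of clarity, not an error. Its numerical effect may be nil and cannot be sized from the document.

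**What to change.** Change the improvement threshold to z ≤ −1.96 and leave the deterioration threshold as it is. This costs one symbol. If the response variable has already been programmed, confirm that the code uses the lower tail.

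Optional, in one or two sentences: call the 7 points an imported criterion, distinct from the trial's own RCI; state the reliability value and its source; and report the sample-based threshold in points beside the 7. Keep 7/53 and 7/47 as the planned recovery criteria. A descriptive count by arm of recovery based on the trial's own RCI with each cut-off could be added from data already collected, but it is not needed. If those versions were tested instead of described, they would add up to four comparisons (two definitions × two time points), for little gain.
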